#### **14.7. Reporting Serious Adverse Events**

Any SAEs considered possibly or probably related to the study drug and discovered by the Investigator at any time after the study should be reported. All SAEs must be reported to the Sponsor within 24 hours of the first awareness of the event. The Investigator must complete, sign and date the SAE pages, verify the accuracy of the information recorded on the SAE pages with the corresponding source documents, and send a copy to the Sponsor.

Additional follow-up information, if required or available, should all be emailed or faxed to the Sponsor within one business day of receipt and this should be completed on a follow-up SAE form and placed with the original SAE information and kept with the appropriate section of the eCRF and/or study file.

The Sponsor is responsible for notifying the relevant regulatory authorities of certain events. It is the Investigator's responsibility to notify the IEC of all SAEs in accordance with the IEC's SAE reporting policy. The Investigator will also be notified of all unexpected, serious, drug related events that occur during the clinical trial. The investigational site is responsible for notifying its IEC of these additional SAEs.

#### **14.8. Follow-up of Adverse Events and Serious Adverse Events**

All AEs and SAEs that are deemed related, possibly related or probably related to the study drug must be followed until resolution, until the condition stabilizes, until the event is otherwise explained, or until the subject dies or is lost to follow-up. The Investigator is responsible for ensuring that follow-up includes any supplemental investigations as may be indicated to elucidate as completely as practical the nature and/or causality of the AE/SAE. This may include additional laboratory tests or investigations or consultation with other health care professionals.

The Sponsor may request that the Investigator perform or arrange for the conduct of supplemental measurements and/or evaluations. If a subject dies during participation in the study or during a recognized follow-up period, the Sponsor should be provided with a copy of any post-mortem findings, including histopathology.

#### **14.9. Dose Limiting Toxicity**

No dose limiting toxicities are anticipated.

#### **14.10. Randomization Codebreak**

Only in the case of an emergency, when knowledge of the study drug is essential for the clinical management or welfare of a specific subject, should the Investigator unblind a subject's treatment assignment. The unbinding procedures for this study will be according to the [REDACTED] RTSM which includes an unblinding module. However, prior to any unblinding, the Investigator is strongly advised to discuss options with the MM, Sponsor, or appropriate study personnel. The Investigator will record in source documentation, the date and reason for revealing the blinded treatment assignment for that subject and the names and roles of the personnel unblinded. The Local MM should be promptly informed.

## 15. STUDY COMPLETION AND DISCONTINUATION

### 15.1. Subject Withdrawal

In accordance with applicable regulations, a subject has the right to withdraw from the study, at any time and for any reason, without prejudice to his future medical care.

If a subject is withdrawn because of an AE, the Investigator must arrange for the subject to have appropriate follow-up care until the AE is resolved or has stabilized. Unresolved AEs will be followed until the last scheduled follow-up/EOS Visit or until the PI and MM determine that further follow-up is no longer indicated. In addition to AEs, other reasons for removal of subjects from the study might include, but are not limited to, withdrawal of consent, administrative decision by the Investigator or the Sponsor, protocol deviation, or subject noncompliance.

If a subject asks or decides to withdraw from the study, all efforts will be made to complete and report the observations, especially the listed primary and secondary objectives, as thoroughly as possible up to the date of withdrawal. The primary reason for withdrawal will be identified and recorded on the appropriate eCRF, along with the date of withdrawal.

### 15.2. Subject Replacement

Subjects who are enrolled but who do not receive any dose of study drug will be replaced and the replacement subject will receive the same treatment as the subject they are replacing. Subjects who discontinue the study prior to completion of dosing may be replaced at the discretion of the Sponsor.

As the main aim of this study is to generate information on the safety and tolerability of EXN407, subjects who receive dosing with study drug and are subsequently withdrawn from the study for reasons other than safety issues may be replaced at the discretion of the Sponsor and the Investigator.

## 16. TERMINATION OR SUSPENSION OF THE STUDY

The study will be completed as planned unless:

- New information or other evaluation regarding the safety of the study drug and/or treatment indicates a change in the known risk/benefit profile for the drug, such that the risk/benefit is no longer acceptable for subjects participating in the study. This may be determined by the Sponsor, the Investigator, the IEC or regulatory authorities.
- The study is terminated by the Sponsor for administrative reasons.

However, this should be discussed between the relevant parties beforehand and the reason for such decision recorded. Should this occur, all data available will also be recorded in the eCRFs.

If the Sponsor, the IEC, or regulatory authority elects to terminate or suspend the study or the participation of the investigational site, a study-specific procedure for early termination or suspension will be provided by the Sponsor, which will be followed by the investigational site during the termination or suspension of the study.

In the event that the study is terminated early, every effort should be made by the Investigator and investigational site staff to follow AEs and SAEs for all subjects up to a 30-day follow-up period after study termination.

The Investigator should notify the relevant IEC in writing of the study's completion or early discontinuation.

## **17. DIRECT ACCESS TO SOURCE DATA/DOCUMENTS**

### **17.1. Study Monitoring**

Before an investigational site can enter a subject into the study, a representative of the Sponsor will visit the investigational study site to:

- Determine the adequacy of the facilities
- Discuss with the Investigator(s) and other personnel their responsibilities regarding protocol adherence, and the responsibilities of the Sponsor or its representatives. This will be documented between the Sponsor and the Investigator.

The Sponsor has appointed [REDACTED] [REDACTED] to manage and monitor the study to assure them of the adequate conduct of the study and to act as the contact with the investigational site. A study monitor will be identified and will be responsible for liaison with, and support of, the investigational site.

The study monitor and regulatory authority inspectors are responsible for contacting and visiting the investigative site for the purpose of inspecting the facilities and, upon request, inspecting the various records of the study (e.g., eCRFs, essential documentation, and other pertinent data) provided that subject confidentiality is respected

During the study, the monitor will have regular contacts with the investigational site for the following:

- Provide information and support to the Investigator(s)
- Confirm that facilities remain acceptable
- Confirm that the investigational team is adhering to the protocol, that data are being accurately recorded in the eCRFs, and that study drug accountability checks are being performed
- Perform source data verification. This includes a comparison of the data in the eCRFs with the subject's medical records at the hospital or practice, and other records relevant to the study. This will require direct access to all original records for each subject (e.g., clinic charts).
- Record and report any protocol deviations not previously sent to the Sponsor
- Confirm AEs and SAEs have been properly documented on eCRFs
- Confirm any SAEs have been forwarded to the Sponsor and those SAEs that met criteria for reporting have been forwarded to the IEC

The monitor will be available between visits if the Investigator(s) or other staff needs information or advice.

## **17.2. Data Management**

All data will be recorded in individual source documents. An eCRF will be created by the data management group for recording of the required data in the study database. All eCRF information is to be filled in by site staff. If an item is not available or is not applicable, this fact should be indicated. Blank spaces should not be present unless otherwise directed.

The study monitor will perform source data verification of data entered into the eCRF and raise queries for correction by the site. The data entered into the eCRF will be subject to data validation checks for consistency and completeness by the data management group. Data queries will then be generated and sent to the investigational site for response before the database is locked and released for statistical analysis.

All eCRFs should be maintained on the system with details of any changes logged accordingly.

## **17.3. Audits and Inspections**

Authorized representatives of the Sponsor, a regulatory authority, or an IEC may visit the site to perform audits or inspections, including source data verification. The purpose of a Sponsor audit or inspection is to systematically and independently examine all study-related activities and documents to determine whether these activities were conducted, and data were recorded, analyzed, and accurately reported according to the protocol, GCP guidelines of the ICH, and any applicable regulatory requirements. The Investigator should contact the Sponsor immediately if contacted by a regulatory agency about an inspection.

## 18. STATISTICS

A detailed methodology for the statistical analyses of the data collected in this study will be documented in a statistical analysis plan (SAP), which will be signed off prior to the database lock. All computations will be performed using SAS® version 9.2 (SAS Institute, Cary, NC). Since the primary objective of the study is to evaluate ocular safety and tolerability, no formal hypothesis testing will be performed for any continuous or categorical variables. All statistical analyses will be descriptive in nature and any statistical inference will be carried out according to the analysis plan and interpreted in view of the exploratory nature of the study.

Descriptive statistics (number non-missing values [n], arithmetic mean, SD, 95% confidence interval for mean [where specified], median and range) will be used to summarize continuous variables. Frequencies and percentages will be used to summarize categorical variables. The summaries will be presented by treatment group/cohort and nominal visit/time point (where applicable). Data from the placebo subjects will be pooled (if appropriate).

Baseline demographics and disease characteristics, safety, and [REDACTED] will be summarized descriptively by treatment group and for all subjects combined. Plasma concentrations of EXN407 will be summarized by treatment group and protocol specified time point, and PK parameters calculated where relevant.

Unless stated otherwise, unscheduled data will not be included in the descriptive summaries.

All subject data will be presented in individual subject data listings. Unless otherwise stated, unscheduled visit results will be included in date/time chronological order, within subject listings only. All listings will be sorted by treatment group, subject number, date/time and visit.

### 18.1. Analysis Populations

Subject inclusion into each population will be determined prior to the final analysis.

#### Intent-to-treat population:

All randomized subjects, regardless of whether they receive study drug or not, will be included in the ITT population. It will be based on the treatment assigned to a subject, not what they actually received. All disposition and demographic data analysis will be based on the ITT population. The ITT population will be used for all data listings.

#### Safety population:

The Safety population will comprise all randomized subjects who received any amount of study drug. Summaries, listings, and analyses will be based on the treatment actually received. Screen failures and randomized subjects who did not receive any medication will be excluded from the safety analysis set. The Safety population will be used for the summaries of all safety assessments.

#### Pharmacokinetic population:

The PK population will comprise all subjects who received any dose of the study drug who had no important protocol deviations affecting the PK parameters and have a sufficiently evaluable concentration-time profile to allow determination of at least one PK parameter from among AUC, Cmax or Tmax.

The number of subjects included in each of the defined analysis populations will be summarized. The number and percentage of subjects who completed the study as planned, subjects withdrawn from the study, as well as the primary reason for early termination will be presented.

## **18.2. Demographic Data and Baseline Comparability**

Demographic data will be summarized by treatment group. Demographic data summary will include, but will not be limited to, age, sex and race. Baseline efficacy assessments will be summarized by treatment group and eye (study or contralateral eye). Demographic summaries will be based on the safety population. If the safety population differs significantly from the ITT population, the demographic and disposition summaries will be repeated for the ITT population.

## **18.3. Safety and Tolerability**

All safety assessments, including concomitant medications, AEs, laboratory evaluations, vital signs, ECGs, and other safety assessments, will be analyzed using the Safety population.

### **18.3.1. Prior and Concomitant Medication**

Prior medications are defined as any medication where the use was stopped prior to the first administration of the study medication.

Concomitant medications are defined as any medication (other than the study drug) that was used at least once after the first administration of the study medication. Medications that were stopped on the same date as the first study drug administration will be analyzed as concomitant medications. If a clear determination cannot be made (partial medication end dates) the medication will be classified as concomitant.

Prior and concomitant medications will be coded using the most current version of the WHO drug dictionary available at the start of the study. Prior and concomitant medications will be listed by subject and concomitant medications summarized by Anatomical Main Group [1st level of the ATC classification], and preferred name and by treatment group using the Safety population.

### **18.3.2. Adverse Event**

AEs will be coded using the most current version of the Medical Dictionary for Regulatory Activities (MedDRA®) available at the start of the study. Treatment emergent adverse events (TEAEs) will be defined as AEs that occurred or worsened following the first administration of study medication. TEAEs will be summarized separately for ocular and non-ocular TEAEs by study and contralateral eye. The number of subjects experiencing TEAEs and the number of individual TEAEs will be summarized by treatment group, study and contralateral eye, system, organ, class (SOC) and PT, including summaries by severity and relationship to study drug.

### **18.3.3. Laboratory Evaluations**

Descriptive statistics of observed values and changes from baseline will be presented for clinical laboratory (hematology, biochemistry and coagulation) by treatment group and visit (descriptive continuous data analysis).

Urinalysis results (normal and abnormal) will be tabulated by treatment group and visit in frequency tables (descriptive categorical data analysis).

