## 7.2. Endpoints

### 7.2.1. Safety and Tolerability

The safety and tolerability endpoints of the study are:

- Primary:
  - Frequency and severity of ocular AEs in the study and contralateral eyes
- Secondary:
  - Frequency and severity of non-ocular AEs
  - Changes from baseline in safety parameters, including vital sign measurements, physical examination findings, ECG, and laboratory parameters
  - Changes from baseline in ophthalmic examination findings, including ophthalmoscopy.

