### **9.1. Subject Inclusion Criteria**

Subjects eligible for enrolment in the study must meet all of the following criteria at Screening and enrolment.

1. Subject is at least 18 years of age inclusive, at the time of signing the informed consent
2. BCVA better than or equal to a 69 ETDRS score (an approximate Snellen equivalent of 20/40 or 6/12) in the study eye using the ETDRS visual acuity scale at Screening or BCVA less than a 69 ETDRS score (an approximate Snellen equivalent of 20/50 or 6/15) but who, in the Investigator's opinion, is unsuitable for treatment with anti-VEGF by intravitreal injection or refuses it. Subjects should have no more than a 7-letter difference in BCVA at Screening and baseline visit.
3. A female subject is eligible to participate if she agrees to use highly effective contraceptive measures (if heterosexually active and a WOCBP) from Screening until study completion, including the follow-up period. Acceptable methods of contraception include the use of condoms AND the use of an effective contraceptive that includes:
  - a. Oral contraceptives (The Pill),
  - b. Long-acting implantable hormones,
  - c. Injectable hormones,
  - d. A vaginal ring or an IUD.Rhythm methods are not considered as highly effective methods of birth control.
4. A female subject must also not be breast feeding and must have a negative pregnancy test prior to start of dosing if of childbearing potential, or must have evidence of non-childbearing potential by fulfilling one of the following criteria at Screening:
  - e. Is postmenopausal defined as aged more than 50 years and amenorrheic for at least 12 months following cessation of all exogenous hormonal treatments.
  - f. Can provide documentation of irreversible surgical sterilization by hysterectomy, bilateral oophorectomy or bilateral salpingectomy but not tubal ligation.
  - g. Is amenorrheic for 12 months and serum follicle-stimulating hormone levels in the postmenopausal range for the institution.
5. Sexually active male subjects where the sexual partner is a WOCBP must be willing to use barrier contraception i.e., condoms, and another acceptable form of contraception (see Inclusion Criteria 3 for acceptable forms) during the study and for 3 months after the last dose of study medication.

6. Diabetes mellitus (Type 1 or Type 2). Any of the following will be considered to be sufficient evidence that diabetes is present:
  - a. Current regular use of insulin for the treatment of diabetes

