8. The following procedures will exclude a potential subject if conducted within 180 days of planned first Screening Visit:
  - a. Intraocular surgery in the study eye
  - b. Laser photocoagulation in the study eye
9. Prior or current use of any systemically administered anti-angiogenic agent (e.g., bevacizumab, sunitinib, cetuximab, sorafenib, pazopanib), approved or investigational
10. Uncontrolled diabetes as indicated by HbA1c  $>12\%$  at Screening or if HbA1c is  $\leq 12\%$  and diabetes mellitus is uncontrolled in the opinion of the Investigator
11. Poorly controlled hypertension at Screening despite lifestyle modifications and pharmacotherapy; systolic blood pressure  $\geq 180$  mmHg or diastolic blood pressure  $\geq 110$  mmHg (mean of 3 measurements according to protocol specified conditions)
12. Current severe heart failure (New York Heart Association class III or IV)
13. QTcF  $>480$  msec in any subject including those with Bundle Branch Block
14. History of (within 90 days of Screening date) cerebral vascular accident (stroke) or MI
15. Current liver disease, known hepatic or biliary abnormalities (with the exception of Gilbert's syndrome or asymptomatic gallstones, with concurrence from the Sponsor study responsible physician) or evidence of abnormal liver function tests [total bilirubin or alkaline phosphatase  $>2 \times$  ULN; or ALT or AST  $>3 \times$  ULN] or other hepatic abnormalities that in the opinion of the Investigator would preclude the subject from participation in the study

16. Significant renal impairment including subjects on chronic renal dialysis and subjects with a history of nephrectomy or kidney transplant (regardless of renal function)
17. History of anaphylaxis, anaphylactoid (resembling anaphylaxis) reactions, or severe allergic responses
18. History of sensitivity to fluorescein, any of the study medications, or components thereof or a history of drug or other allergy that, in the opinion of the Investigator or the study MM ( [REDACTED] or Sponsor MM, contraindicates subject participation
19. Use of another IP within 1 month or 5 half-lives or twice the duration of biological effect (whichever is the longest) preceding the first dose of study medication

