#### **14.1.6.    Laboratory Assessments**

Safety laboratory tests (hematology, biochemistry, coagulation, and urinalysis) will be performed at the time points specified in the Schedule of Assessments ([Table 5](#)). Additional clinical laboratory tests may be performed at other times if deemed necessary based on the subject's clinical condition.

Medically indicated laboratory tests (emergency / unscheduled tests) can be conducted at the local laboratory, however blood samples from all unscheduled draws should also be sent to the central laboratory.

A blood sample will be taken from each subject for hematology, coagulation and biochemistry analyses at the time points delineated in the study schedules.

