#### **14.1.6.4. Urinalysis**

A urinalysis test (dipstick) will be performed for each subject. Urinary analysis will be performed at Screening and other times according to the study schedule. If abnormality is noted for protein, blood, nitrite or leukocyte esterase (and at the discretion of the Investigator) a microscopic examination of RBC, WBC, bacteria and casts will be performed.

Macroscopic urinalysis parameters to be tested are:

- pH (PH)
- Specific Gravity (SPGRAV)
- Creatinine (CREATININE)
- Protein (PROT)
- Glucose (GLUC)
- Ketones (KETONES)
- Total Bilirubin (BILI)

- Occult Blood (OCCBLD)
- Nitrite (NITRITE)
- Urobilinogen (UROBIL)
- Leukocytes (WBC)

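### Urinalysis is summarized only as normal/abnormal counts by visit, so the summary table cannot show change from baseline in subjects who enter with an abnormal result

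*Combined protocol and SAP*

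**What the plan says.** Section 7.2.1 lists as a secondary endpoint "Changes from baseline in safety parameters, including vital sign measurements, physical examination findings, ECG, and laboratory parameters". Section 14.1.6 includes urinalysis in the laboratory panel: "Safety laboratory tests (hematology, biochemistry, coagulation, and urinalysis) will be performed at the time points specified".

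Section 18.3.3 then treats the panels differently. For three of them, "Descriptive statistics of observed values and changes from baseline will be presented for clinical laboratory (hematology, biochemistry and coagulation) by treatment group and visit". For the fourth, "Urinalysis results (normal and abnormal) will be tabulated by treatment group and visit in frequency tables (descriptive categorical data analysis". No baseline comparison, shift table or grade is mentioned for urinalysis.

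Section 14.1.6.4 gives the method ("A urinalysis test (dipstick) will be performed for each subject") and an eleven-item panel that includes protein, glucose, ketones, occult blood, leukocytes, pH and specific gravity. Table 5 schedules urinalysis at Screening and Day 1 in both parts of the study. After that it is done on Days 8 and 36 in the escalation cohorts, and on Days 8, 29, 57, 85 and 113 in the expansion cohort. A baseline value and repeated later values are therefore collected for each subject.

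**The concern.** An endpoint defined as change from baseline needs a summary that links each later result to the same subject's baseline. The urinalysis rule has no such link. It reduces each result to two levels and counts them separately at each visit.

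That loses most in subjects who are already abnormal on Day 1. Section 9.1 requires diabetes in every subject ("Diabetes mellitus (Type 1 or Type 2"), and Section 9.2 sets the fixed HbA1c exclusion only above 12%. Abnormal urine protein or glucose at entry is therefore plausible for some subjects. In them a further rise in protein or occult blood would not move the count. Systemic safety is a secondary objective of this first-in-human study, and the table meant to summarize this panel by treatment group could look flat while results within the abnormal category get worse.

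**Working it through.** The documents give no urinalysis distribution, effect size or error rate for this point, so there is no planned figure to reproduce. The check sets the sections side by side and then counts what a two-level table can show.

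**Endpoint against analysis**

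| Panel | Safety laboratory test (14.1.6) | Change-from-baseline summary (18.3.3) |
|---|---|---|
| Hematology | yes | yes |
| Biochemistry | yes | yes |
| Coagulation | yes | yes |
| Urinalysis | yes | no, normal/abnormal count only |

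The mismatch follows from the text without any assumption.

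**What the count can show.** Inputs:
- Expansion cohort of up to 40 subjects randomized 2:1 (Section 6.4.3): 40 × 2/3 = 26.7, so about 27 on EXN407 and 13 on vehicle.
- Dipstick results coded 0 for normal and 1 to 4 for abnormal. This coding is hypothetical, since Section 14.1.6.4 gives no scale.
- 18 of the 27 abnormal at baseline (nine at 0, nine at 1, nine at 2). This too is hypothetical.

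*Example 1.* All 18 abnormal subjects worsen (1 to 2, and 2 to 4). The table reads 18/27 at baseline and 18/27 afterwards, exactly as it would with no change. A graded shift table would show 18 subjects worsening.

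*Example 2.* Five subjects go from normal to abnormal and five from abnormal to normal: 18 + 5 − 5 = 18. The table again reads 18/27 at both visits. A shift table would show five in each direction.

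**Share hidden.** Let b be the proportion abnormal at baseline and w the proportion who worsen, with w the same whatever the baseline status. Then:
- expected worsenings = n × w
- visible in the count = n × w × (1 − b)
- hidden = n × w × b

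Hidden divided by total is b, whatever w is. For n = 27 and an assumed w = 0.30, n × w = 8.1:

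| Assumed b | Visible | Hidden |
|---|---|---|
| 0.20 | 6.5 | 1.6 |
| 0.40 | 4.9 | 3.2 |
| 0.60 | 3.2 | 4.9 |
| 0.80 | 1.6 | 6.5 |
| 0.95 | 0.4 | 7.7 |

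Both b and w are assumptions. The table shows how the loss scales and does not forecast this trial. The visible column is also a best case, because subjects who normalise would offset some of it.

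**Per analyte or overall.** Section 18.3.3 does not say whether the normal/abnormal flag is set per analyte or once for the whole dipstick. One overall flag makes b larger. With assumed rates of 40% for protein and 50% for glucose, taken as independent, 1 − (1 − 0.40)(1 − 0.50) = 0.70. The conclusion holds either way.

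**The case against.** The strongest case against is that the plan has other routes to the same information.

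- **Adverse events.** Section 14.5 names urinalysis among the laboratory findings and counts as adverse events those clinically significant abnormalities that were there at baseline and later worsen. Section 18.3.2 includes worsening in its definition of a treatment-emergent event and summarizes these by treatment group, severity and relationship. This stands. It leaves out only worsening that is not judged clinically significant and has no associated signs or symptoms.
- **Biochemistry.** Serum glucose, HbA1c and creatinine are in the panel of Section 14.1.6.2 and do get change-from-baseline summaries. This largely covers glucose. It does not cover urine protein, occult blood or leukocytes.
- **Listings.** Section 18 lists all data by subject in date order. With about 48 subjects planned, a reader can follow serial values. Listings still do not summarize by treatment group.
- **Eligibility.** Section 9.2 also excludes subjects at or below 12% HbA1c whose diabetes the Investigator considers uncontrolled, and excludes significant renal impairment. Both may lower the rate of abnormal baselines, but neither sets a urine protein limit.
- **Deferred detail.** Section 18 leaves detailed methods to a separate SAP that is not in the supplied text and could add a shift table. Section 18.3.3 is nevertheless the only explicit urinalysis rule available, and a SAP author would start from it.

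A reader might infer that no summary at all would reveal worsening, that the population is known to be abnormal at entry, or that the plan gives false reassurance on systemic safety. The documents support none of these. The adverse event tables are a summary by treatment group, no baseline urinalysis rate is given, and under Section 8.4 dose recommendations rest on committee review of available clinical and laboratory safety data, not on this table.

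**Conclusion.** The point holds in a narrow form. Section 18.3.3 gives urinalysis no change-from-baseline summary although the endpoint in Section 7.2.1 calls for one. A two-level count by visit cannot show worsening within the abnormal category, or opposite shifts that cancel. New abnormality in subjects normal at baseline can still show.

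What goes unsummarized is mainly worsening in urine protein, blood and other dipstick items that is not judged clinically significant. The data are collected and listed, so the gap lies in the summary only.

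No size can be drawn from the documents. The statement that the hidden share equals the baseline abnormal rate assumes that worsening is independent of baseline status. That abnormal baselines occur at all is a reasonable inference from the diabetic population and is not documented. It would also be tempting to express the loss as power to detect a treatment difference. That would need an assumed worsening rate and a significance test, and Section 18 plans no formal testing, so no such figure is offered.

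Severity is low: a useful improvement to one table in a descriptive study.

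**What to change.** In Section 18.3.3, and in the SAP, add to the urinalysis sentence along these lines:

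- For each categorical dipstick analyte (such as protein, glucose, ketones, occult blood and leukocytes), present a shift table by treatment group from Day 1 to each later visit and to the worst post-baseline result. Use the dipstick category as reported, or normal/abnormal where no grade is captured.
- Summarize pH and specific gravity as continuous variables, at each visit and as the difference from Day 1.
- Keep the normal/abnormal table if wanted, and state whether its flag is per analyte or overall.

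Before finalizing, confirm that the eCRF or laboratory transfer holds the reported dipstick category. A normal/abnormal shift table would restore the shifts that cancel in the current table, but not worsening within the abnormal category.

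The change needs no new samples, visits or subjects. It costs a wording change and a few more table pages, with sparse cells in the 3-subject dose groups.
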